3. ABBREVIATIONS

AE	Adverse Event
BMI	Body Mass Index
BP	Blood Pressure
CI	Confidence Interval
CI	Chief Investigator
CTU	Clinical Trials Unit
DBP	Diastolic Blood Pressure
DCF	Data Collection Form
GCP	Good Clinical Practice
GP	General Practitioner
HDP	Hypertensive Disorders in Pregnancy
HDU	High Dependency Unit
ISF	Investigator Site File
ITU	Intensive Therapy Unit
LCM	Local Co-ordinating Midwife
MHRA	Medicines and Healthcare Products Regulatory Agency
NICE	National Institute of Clinical Excellence
NICU	Neonatal Intensive Care Unit
NIHR	National Institute Health Research
OC	Oversight Committee
OR	Odds Ratio
PIS	Patient Information Sheet
PMG	Project Management Group
QALY	Quality Adjusted Life Year
R&D	Research and Development
RR	Relative Risk
RVI	Royal Victoria Infirmary, Newcastle
SACr	Spot Albumin Creatinine ratio
SAE	Serious Adverse Event
SBP	Systolic Blood Pressure
SOP	Standard Operating Procedure
SoPC	Summary of Product Characteristics
SPCr	Spot Protein Creatinine ratio
SUSAR	Suspected Unexpected Serious Adverse Reaction
UK	United Kingdom

4. PROTOCOL SUMMARY

Short title:	DAPPA
Protocol version:	2.0
Protocol date:	7 th April 2015
Chief Investigator:	[name]
Sponsor:	The Newcastle upon Tyne Hospitals NHS Foundation Trust
Funder:	NIHR Health Technology Assessment programme
Study design:	Prospective cohort study to evaluate the diagnostic accuracy of SPCr and SACr in comparison with 24 hour proteinuria in hypertensive pregnant women with suspected proteinuria. We will also undertake decision analytic modeling and cost effectiveness analysis.
Primary objective:	To evaluate the diagnostic accuracy of quantitative assessments of SPCr and SACr (index tests) at different thresholds in predicting severe PE compared to 24 hour urine protein measurement
Secondary objectives:	
To assess the accuracy of point of care assessments of SPCr and SACr at different thresholds in diagnosing PE compared to 24 hour urine protein measurement
 
To identify the laboratory assay method of 24 hour proteinuria that is most accurate in the assessment of PE
 
To estimate the accuracy of both quantitative and point of care assessments of SPCr and SACr at different thresholds in predicting adverse fetal outcomes
 
To estimate the diagnostic utility of SPCr or SACr as a potential replacement for 24 hour protein estimation by developing a decision analytic model
 
To assess the cost effectiveness using cost per correct diagnosis and cost per adverse outcome predicted as key measures

Primary outcome:	Severe PE as defined by NICE [5]
Number of study sites:	Up to 36
Study population/size:	1790
Study duration:	44 months

5. BACKGROUND

5.1 Clinical Background

Preeclampsia is a multisystem disorder of pregnancy associated with raised blood pressure and proteinuria. Hypertensive disorders in pregnancy (HDP) remain the second leading cause of direct maternal deaths in the UK and account for 20% of all stillbirths [9, 10]. One in 5 women with hypertension is diagnosed with PE, resulting in complex treatment and substantial health care costs [5]. Women with severe PE require high dependency care. Preeclampsia is also responsible for significant infant morbidity related to fetal growth restriction and prematurity resulting in prolonged neonatal intensive care treatment and lifelong handicaps; the additional NHS costs to care for a preterm baby born before 33 weeks and 28 weeks are £61,509 and £94,190 respectively [5]. £939 million in extra costs for care of preterm babies per year in the NHS are linked to neonatal care such as incubation, and hospital readmissions [5].

The potential impact of early and accurate assessment of PE is enormous. The reliable diagnosis of significant proteinuria is critical in women with gestational hypertension because it distinguishes between those with PE from those with isolated hypertension; this distinction determines future monitoring and management. Furthermore, the determination of the most appropriate threshold for abnormal proteinuria that predicts clinical outcome helps to better focus resource on high risk women and reduce unnecessary iatrogenic intervention. Currently women with suspected PE undergo 24 hour proteinuria testing mostly as in-patients to evaluate the severity of the condition. The cost associated with 24-hour protein measurement and additional testing needs to be evaluated against identifying women with PE and avoiding the mortality, morbidity and costs associated with undiagnosed PE.

NICE acknowledges the paucity of evidence relating to the diagnosis of significant proteinuria and the unclear prognostic value of various urinary protein thresholds [5]. They have highlighted the need for “large, high-quality prospective studies comparing the various methods of measuring proteinuria (automated reagent-strip reading devices, urinary protein : creatinine ratio, urinary albumin : creatinine ratio, and 24-hour urine collection) in women with new-onset hypertensive disorders during pregnancy” [5].

Our proposed study aims to address this shortfall in evidence by determining which method of measurement, and which diagnostic thresholds, are most accurate in predicting not just PE, but more importantly, clinically significant outcomes. This will help to inform decisions regarding clinical management of gestational hypertensive disorders during pregnancy.

5.2 Description of Technology

Index tests: Proteinuria estimation by urinary SPCr or urinary SACr in women with suspected PE is available as either a laboratory or point of care (POC) test. The POC SPCr and SACr are measured by urine reagent strip analysis on a semi-quantitative automated reader. SACr can also be measured on a fully quantitative device configured in a plastic cassette, the reaction being monitored in a benchtop photometer. These technologies are already in clinical use for screening albuminuria (and microalbuminuria) and proteinuria in both chronic kidney disease and diabetes.

Comparative test: Measurement of 24-hour urine protein is currently the gold standard for the assessment of proteinuria in pregnancy. However this test is associated with

significant costs related to hospital admission, as often women are admitted as an inpatient for up to 48 hours until the results become available. Furthermore, the measurement is subject to errors (in as many as 20% of patients) as a result of incomplete collection. Diagnosis of proteinuria in HDP also varies with the type of laboratory assay used [4].

A reliable, accurate and cost effective SPCr or SACr ratio test (laboratory or POC), that is equivalent or better than 24 hour protein estimation at predicting adverse maternal and fetal outcomes, could be employed as the primary test in the assessment of women with suspected PE. Furthermore, given the rising costs of inpatient care, the use of SPCr or SACr has the potential to deliver significant cost improvements. A clearer understanding of the threshold of proteinuria (by any measurement) that predicts increased risks of adverse maternal and fetal outcomes will allow the concentration of scarce NHS resource onto the more intensive monitoring of fewer women.

5.3 Summary of current evidence

Current recommendations for assessment of proteinuria vary. Recently published NICE guidelines in the UK suggest the use of automated reagent-strip reading device to detect proteinuria. In women with a result of 1+ or more, the use of spot SPCr or 24 hour urine collection is recommended to quantify proteinuria. Significant proteinuria is defined as SPCr greater than 30 mg/mmol or a validated 24-hour urine collection greater than 300 mg/24 hour. Where 24-hour urine collection is used to quantify proteinuria, a recognized method of evaluating completeness of the sample is recommended [5]. The Society of Obstetricians and Gynaecologists of Canada suggests using urinary dipstick testing to screen for proteinuria, with the definition of significant proteinuria similar to NICE guidelines [11]. The American College of Obstetricians and Gynaecologists consider 24 hour urine protein estimation of more than 300 mg as significant proteinuria for a diagnosis of PE [12].

5.4 Work leading to the trial

- *Diagnostic accuracy of SPCr / SACr in assessing proteinuria in women with HDP.*

Price et al [13] in 2005 and Cote et al [14] in 2008 performed a systematic review of 1214 women with gestational hypertension. SPCr, with a cut-off of 30 mg/mmol, had pooled sensitivity of 83.6% (95% CI 77.5-89.7%), specificity 76.3% (72.6-80.0%), likelihood ratio positive (LR+) 3.53 (2.83-4.49), and LR- 0.21 (0.13-0.31). Both authors concluded that SPCr was a reasonable “rule-out” test for proteinuria of 300 mg/day or more in HDP. However, laboratory assays in the primary studies were not well described. This led to the recommendation for future studies on SACr to predict significant proteinuria and clinical outcomes.

- *Evaluation of proteinuria thresholds and assays in predicting adverse clinical outcomes.*

The applicants have assessed the use of different laboratory assays to measure 24 hour proteinuria in pregnancy [4, 8]. The prevalence of proteinuria >300 mg/24 hour and hence the prevalence of PE differed between the two assays studied, (24.9% for Bradford assay (BA) and 70.1% for Benzethonium chloride assay (BCA)). The threshold of 300 mg/24 hours performed poorly as a predictor of adverse outcomes [15]. At the 500 mg/24 h threshold BCA assay predicted severe hypertension with an LR+ of 1.51 (95%CI 0.99-2.28) and small for gestational age with a LR+ of 1.72

(95%CI 1.11-2.66). However at the 500 mg/24 hour threshold the LR+ for BA for severe hypertension was 2.15 (95%CI 1.07-4.34), birthweight <10th centile (LR+: 2.79 95%CI 1.4-5.54) and biochemical disease (LR+: 2.47 95%CI 1.22-5.01). This data supports the recommendation from NICE for prospective studies to explore the relationship between individual assays for proteinuria and clinical outcome.

- *Point of care measurement of proteinuria.*

The applicants have also investigated point of care (POC) testing for proteinuria and albuminuria in pregnancy and PE [6]. SACr dipsticks and fully quantitative SACr were compared with 24 hour proteinuria [7]. Dipstick SACr testing did not improve detection rates whether automated or visual. Fully quantitative measurement of SACr was a better predictor than any dipstick technique; LR+ 14.6 (95% CI 6.74-31.8), LR- 0.069, (95% CI 0.030-0.16) [7]. In a systematic review of 6 studies of visual dipstick analysis, Waugh et al. [16] reported a pooled LR+ 3.48 (95% CI 1.66, 7.27) and a pooled LR- of 0.6 (95% CI 0.45, 0.8) for predicting 300 mg/24-hour proteinuria at the 1+ or greater threshold. We concluded that the accuracy of dipstick urinalysis with a 1+ threshold in the prediction of significant proteinuria is poor and therefore of limited clinical value [16].

The POC technology proposed for study in this trial has been validated by the applicants [6]. We have also determined the reference range for SACr in the normal pregnant population [17]. Our study comparing semi-quantitative and fully quantitative POC tests for albuminuria and proteinuria found automated dipstick urinalysis to have better predictive values for significant proteinuria (LR+ 4.27, 95% CI 2.78 to 6.56; LR- 0.225, 95% CI 0.14 to 0.37) compared to conventional visual dipstick urinalysis (LR+ 2.27, 95% CI 1.47 to 3.51; LR- 0.635, 95% CI 0.49 to 0.82). Dipstick microalbumin/creatinine ratio testing did not improve overall detection rates with automated or visual testing. Fully quantitative POC of ACR was better than any dipstick technique (LR+ 14.6, 95% CI 6.74 to 31.8; LR- 0.069, 95% CI 0.030 to 0.16) [7]. These studies have informed the development of NICE CG 107 [5]: Assessment of Proteinuria in (HDP) and the development of the protocol.

- *Systematic review of tests that predict onset of preeclampsia.*

We have evaluated the accuracy of tests in predicting onset of PE by a systematic review of the literature (HTA No. 01/64/04). This study concluded that no current tests employed in screening for pre-eclampsia were sufficiently accurate or effective to become part of routine care. One of the recommendations from that project was to evaluate prognostic/predictive features like proteinuria that are associated with maternal and foetal complications once PE has started.

- *Systematic reviews on the accuracy of tests to predict complications in preeclampsia – TIPPS (Tests in the Prediction of Pre-eclampsia Severity) project.*

We have conducted systematic literature reviews to assess the predictive value of five of the commonly performed tests in PE. We analysed more than 25,000 citations and reviewed 60 relevant studies. Although we conducted good quality reviews including one on proteinuria it was hard to provide recommendations on the value of tests due to the deficiencies in the primary studies. However the data collated give face validity of the choice of tests that have been chosen for use in the proposal [15].

- *Development and validation of a Prediction model for Risk of complications in Early onset Pre-eclampsia (PREP).*

We have recently been funded by HTA to undertake the first prognostic study to develop a prediction rule for adverse outcomes in early onset PE that will provide personalised estimates of maternal and foetal risks. The PREP study will achieve this by validating the model in two prospective external datasets in Netherlands and Canada. The data from PREP will complement the proposed project in evaluating the association between proteinuria and adverse outcomes. Furthermore it will also provide valuable data on outcomes of women with severe PE to further populate the decision analytic model for economic evaluation.

6. AIMS OF THE STUDY

Our proposed study evaluates the measurement of proteinuria in women with suspected preeclampsia (PE). This includes women with gestational hypertension $\geq 140/90$ mmHg and \geq Trace proteinuria on automated dipstick analysis.

Primary Objectives:

1. To evaluate the diagnostic accuracy of quantitative assessments of SPCr and SACr (index tests) at different thresholds in predicting severe PE compared to 24 hour urine protein measurement

Secondary Objectives:

2. To assess the accuracy of point of care assessments of SPCr and SACr at different thresholds in diagnosing PE compared to 24 hour urine protein measurement
3. To identify the laboratory assay method of 24 hour proteinuria that is most accurate in the assessment of PE
4. To estimate the accuracy of both quantitative and point of care assessments of SPCr and SACr at different thresholds in predicting adverse fetal outcomes
5. To estimate the diagnostic utility of SPCr or SACr as a potential replacement for 24 hour protein estimation by developing a decision analytic model
6. To assess the cost effectiveness using cost per correct diagnosis and cost per adverse outcome predicted as key measures

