7.2 Secondary clinical outcomes

Maternal: Diagnosis of PE using a 24 hour proteinuria threshold of 300 mg/24 h

Fetal: Composite adverse perinatal outcome identified by Delphi survey of clinicians. This includes one or more of the following: perinatal or infant mortality, bronchopulmonary dysplasia, necrotising enterocolitis, grade III/IV intraventricular haemorrhage, cystic periventricular leukomalacia, or stage 3-5 retinopathy of prematurity and hypoxic ischaemic encephalopathy.

Costs: Health service data on bed use, surveillance visits as an inpatient, outpatient and peripartum health service resource use related to delivery, postnatal care and follow-up tests will be collected by the research midwife following delivery. These will include resource use for neonatal care. (see section 7: Economic evaluation).

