8. HEALTH TECHNOLOGIES BEING ASSESSED

8.1 Index tests

Laboratory quantitative tests (Laboratory SPCr and SACr)

Urinary protein will be measured using a benzethonium chloride turbidimetric method in all recruiting hospitals. The reagent acts as a denaturing agent causing the formation of a fine suspension in the reaction mixture. The analytical range for the Benzethonium chloride assay is 68 to 2000 mg/L and the day-to-day precision is 1.4 – 3.0%.

The SACr will be measured using an automated chemistry analyzer. Albumin is measured using an immunoturbidimetric immunoassay. The analytical range of the assay is 5 to 500 mg/L, and the day-to-day precision is within the range 2.5 – 5.0%. The analytical range of the assay is 0.3 to 44.2 mmol/L and the day-to-day precision is between 1.5 – 3.0%.

The urine creatinine will be measured using an enzymatic reaction, in which creatininase hydrolyses creatinine to creatine, which is itself hydrolysed by creatinase to sarcosine and urea. The analytical range of the assay for SPCr is 0.3 to 44.2 mmol/L and the day-to-day precision is between 1.5 – 3.0%.

Point of Care tests (Semi quantitative reagent strip SACr).

The dipstick test for ACR comprises two test pads, the colours formed in the presence of albumin and creatinine being read using a reflectance meter; the system provides a semi-quantitative result. The detection of albumin is based on binding of Bis (3',3''-diiodo-4',4''-hydroxy-5',5''-dinitrophenyl)-3,4,5,6-tetrabromosulfonephthalein (DIDNTB) at pH 1.5. It has been shown to be specific for the detection of albumin. The detection limit of the method is 0.9 mmol/L (10 mg/dl). The ACR is reported as one of the following ranges in conventional units (mg/g): <30, 30-300; or >300; or one of the following ranges in SI units (mg/mmol): <3.4, 3.4-33.9, or >33.9.

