12.2 Analysis

We aim to show that a quantitative assessment of SPCr or SACr can safely rule out the possibility of adverse outcomes. Diagnostic accuracy of laboratory and POC care measurements of SPCr and SACr at given cut-offs will be summarised using sensitivity, specificity, and positive and negative likelihood ratios, estimated using standard methods for proportions. Sensitivity and specificity at different cut-offs will be used to plot non-parametric receiver operating characteristic (ROC) curves for the different assays. Laboratory quantitative assessments of SPCr and SACr, POC are assays, and laboratory measures of 24-hour urine protein will be compared by looking at the difference between the areas under the respective ROC curves. Caution should be exercised if an ROC curve is used to select an “optimal” cut-off for a continuous test measure without validation in a separate sample. We will use our sample to validate cut-offs identified in previous research [7]. By restricting analyses to those women with 1+ or higher on the automated dipstick test, we will evaluate test performance in the population of women who would currently be referred for further testing. Because we may wish to consider making testing more inclusive, we will also analyse our entire sample to evaluate test performance in women with trace or higher on the automated dipstick test.

In addition we will use linear regression to explore the relationship between each SPCr/SACr measurement and the local measurement of 24-hour proteinuria (“linear” regression in the sense of a Normal model with linear link function; we will have a large enough sample to investigate non-linear associations between SPCr/SACr and 24-hour proteinuria). In particular, we will investigate whether the relationship is different at sites using different 24-hour assays, and whether these differences might be explained by measured patient characteristics. If there are differences between sites, our primary analysis of diagnostic accuracy will be stratified by the type of 24-hour assay used. To make use of the full sample, and to try and obtain more generalizable results, we will also fit multivariable logistic regression models for predicting outcomes using SPCr/SACr, site, and patient characteristics.

All analyses will be carried out using Stata v11 (Stata Corporation, College Station, Texas USA).

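### Objective 3 seeks the most accurate 24-hour protein assay, but the one accuracy comparison stated for 24-hour measures, ROC area, cannot show whether two assays classify women differently at 300 mg/24 h

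*Protocol*

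**What the plan says.** Section 6 sets objective 3: "To identify the laboratory assay method of 24 hour proteinuria that is most accurate in the assessment of PE". Section 7.2 fixes the maternal secondary outcome as "Diagnosis of PE using a 24 hour proteinuria threshold of 300 mg/24 h", one threshold whatever the assay. The primary outcome in section 7.1 uses the same 300 mg figure.

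Section 5.4 motivates the assay question with the applicants' earlier data. The share of women above 300 mg/24 h was "24.9% for Bradford assay (BA) and 70.1% for Benzethonium chloride assay (BCA". It then gives positive likelihood ratios for the two assays at 500 mg.

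Section 8.2 names benzethonium chloride and pyrogallol red as the methods for this study. It says their variation in performance will be examined, but names no measure.

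Section 12.2 says that spot tests, point-of-care assays and "laboratory measures of 24-hour urine protein will be compared by looking at the difference between the areas under the respective ROC curves". The sentence on accuracy at fixed cut-offs covers only "measurements of SPCr and SACr at given cut-offs will be summarised using sensitivity, specificity, and positive and negative likelihood ratios". A later regression relates SPCr/SACr to local 24-hour protein, and "we will investigate whether the relationship is different at sites using different 24-hour assays". If sites differ, "our primary analysis of diagnostic accuracy will be stratified by the type of 24-hour assay used". Section 8.1, however, states: "Urinary protein will be measured using a benzethonium chloride turbidimetric method in all recruiting hospitals".

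**The concern.** The difference reported in section 5.4 appears at a fixed clinical threshold: the same 300 mg rule labels very different shares of women depending on the assay. ROC area asks something else, namely how well an assay orders women with and without the outcome. Two assays can order women identically and still disagree about who exceeds 300 mg. With ROC area as the stated comparison, objective 3 could be reported as showing no difference in accuracy while the assays give different PE diagnoses to the same women. Laboratories would then learn nothing from this objective about the threshold at which PE is diagnosed.

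**Working it through.** **Inputs from the protocol.** Shares above 300 mg/24 h: 24.9% (Bradford) and 70.1% (benzethonium), section 5.4. Outcome prevalence for illustration: 15.6%, the proxy prevalence of severe PE in section 12.1. The two shares are cited results without raw data, so they cannot be reproduced from the protocol.

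**Assumptions, not in the protocol.** Log protein is Normal with equal SD in women with and without the outcome. One assay reads a constant multiple of the other. The outcome is not defined by either assay. The AUC is 0.65, 0.75 or 0.85.

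**Step 1: what ROC area can see.** AUC = P(case value > non-case value) + ½P(tie). If B = c × A with c > 0, every pairwise ordering is the same for A and B. The AUC difference is exactly 0 for any c, however many women cross 300 mg.

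**Step 2: the shift that the cited pair would imply.** z(0.701) + z(0.751) = 0.527 + 0.678 = 1.205 SD on the log scale. As a multiple this is exp(1.205 × log SD): about 2.1 for a log SD of 0.6 and 4.2 for 1.2. The gap in positivity is 70.1 − 24.9 = 45.2 percentage points.

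**Step 3: accuracy at 300 mg with equal AUCs.** Case separation is d = √2 × z(AUC). The cut-off t solves 0.156 × [1 − Φ(t − d)] + 0.844 × [1 − Φ(t)] = share positive. Sensitivity is 1 − Φ(t − d) and specificity is Φ(t).

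| AUC, both assays | Share ≥300 mg | Sensitivity | Specificity | LR+ | LR− |
|---|---|---|---|---|---|
| 0.65 | 70.1% | 84.1% | 32.5% | 1.25 | 0.49 |
| 0.65 | 24.9% | 40.9% | 78.1% | 1.87 | 0.76 |
| 0.75 | 70.1% | 91.5% | 33.9% | 1.38 | 0.25 |
| 0.75 | 24.9% | 53.8% | 80.4% | 2.75 | 0.57 |
| 0.85 | 70.1% | 96.8% | 34.8% | 1.49 | 0.09 |
| 0.85 | 24.9% | 69.2% | 83.3% | 4.14 | 0.37 |

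The AUC difference is 0 in each pair, while sensitivity differs by about 28 to 43 points. A simulated data set of 1,539 women, with one assay a fixed multiple of the other, gave the same rank-based AUC (0.749) for both. Sensitivity was 53.2% against 91.3%, and specificity 80.1% against 33.6%.

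**Step 4: smaller shifts.** The shift between benzethonium and pyrogallol red is not given. Start from 70.1% positive and let the second assay read lower by s SD, so that its share is Φ(0.527 − s):

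| s (SD) | Share ≥300 mg | Gap (points) |
|---|---|---|
| 0 | 70.1% | 0 |
| 0.25 | 60.9% | 9.2 |
| 0.5 | 51.1% | 19.0 |
| 1.205 | 24.9% | 45.2 |

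ROC area is the same in all four rows.

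**The case against.** **Other planned analyses touch on assays.** Section 12.2 plots curves from sensitivity and specificity at a range of cut-offs, so the 300 mg point could be read off a 24-hour curve. The regression is sensitive to scale. Section 8.2 promises work on variation between the two methods. The economic model in section 12.3 needs true and false positives for 24-hour protein, which implies some threshold. It would therefore be wrong to infer that ROC area is the only assay analysis planned. What stands is narrower: none of these is stated as a comparison of the two assays' accuracy at 300 mg. The regression compares sites and does not rank assays. If section 8.1 holds for 24-hour samples, it has no assay contrast at all.

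**The SAP may add the detail.** It may. But the protocol is not silent: it names a comparison, and that comparison does not fit the objective's threshold.

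**The cited figures concern another pair.** This stands. A reader might infer that 45 in 100 women would be classified differently in this study. The protocol does not support that, because Bradford is not among its assays. That the earlier difference was purely one of scale is also an inference. The positive likelihood ratios at 500 mg in section 5.4 (1.51 against 2.15 for severe hypertension) may reflect scale, ranking or both.

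**A 300 mg comparison could favour one assay.** This stands and shapes the fix. PE and severe PE include proteinuria, and section 8.1 has benzethonium as the local method. Sensitivity and specificity for those outcomes would favour the assay that helped to define them.

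**Threshold-free discrimination is a legitimate meaning of accuracy.** It is. Section 5.4 says 300 mg predicted adverse outcomes poorly, section 5.1 aims to find the best thresholds, and a pure scale shift could be met by assay-specific cut-offs. So ROC area should stay, with the threshold comparison beside it.

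**Conclusion.** The point holds in a limited form. ROC area is the only accuracy comparison that section 12.2 states for 24-hour measures. By construction it cannot show whether benzethonium and pyrogallol red classify women differently at 300 mg/24 h. This rests on a property of ranks and on no assumption about the data.

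The size for this study is unknown. It may be zero. The 45.2-point gap in section 5.4 shows only that assay choice can matter at this threshold; it is not a forecast. The sensitivity and specificity figures above also depend on the assumed AUC, the Normal model, the 15.6% prevalence and an outcome independent of the assay.

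A reader might also infer that the investigators intend to declare the assays equivalent on ROC area. The protocol does not say so. The risk is that a null area difference would be read that way. The issue affects one secondary objective and leaves the primary analysis of SPCr and SACr intact.

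**What to change.** For objective 3, keep the ROC area comparison and add the following for the two total-protein methods on the same 24-hour aliquots:

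1. The paired proportion at or above 300 mg/24 h, with a 95% CI for the difference (McNemar-type), and the paired ratio of results as a measure of agreement.
2. Paired differences in sensitivity, specificity and likelihood ratios at 300 mg, with 95% CIs, for outcomes not defined by either assay's protein result. Examples are severe hypertension, biochemical disease or the perinatal composite in section 7.2.
3. A statement that interchangeability of the assays will not be inferred from ROC area alone.

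Reconcile section 8.1 (benzethonium at all recruiting hospitals) with section 12.2 (sites using different 24-hour assays). Section 8.1 concerns the index tests, so say whether it also governs local 24-hour measurement.

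The cost is analysis wording and a few more tables. Aliquots of the 24-hour urine are already stored (section 9), and both total-protein methods are planned (section 8.2). One check is needed: section 9 describes the batched 24-hour analysis as albumin excretion by two assays, so confirm that both total-protein methods are run on these aliquots. If they are, no new samples, assays or participants are needed.
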